## Statistical Analysis Plan

Descriptive statistics, including means, standard deviations, and ranges for continuous variables, as well as percentages and frequencies for categorical variables, will be provided to describe the study sample. Differences between group means for continuous variables will be examined using ANOVA or Kruskal-Wallis Test. Point estimates along with the corresponding p-values and 95% confidence intervals will be reported. The adjusted p-values and the corresponding 95% confidence interval will be reported for multivariate analyses. Statistical analysis will be done with JMP version 12.0 (SAS Corporation, Cary, NC).

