## 5.0 Enrollment]Randomization

Patient Enrollment: The treating physician will identify potential subjects with a previously implanted Biotronik pacemaker and present a brief overview of the study; if the subject is interested, the study will be described in detail. Informed consent will be obtained by the investigator after discussing the study, including the voluntary nature of participation and notification the subject can withdraw at any time. Ample time for questions and answers will be allowed. The investigator will give the subject and his/her legal guardian the opportunity to take the consent home to think about it more, with the option to call or meet with the investigator to ask additional questions. If the subject and/or his/her parent/legal guardian agree to participate, the investigator will ask them to sign a written, informed consent and assent. A copy of the assent and consent will be given to the subject and/or his/her parent/legal guardian.

Randomization Procedure: This will be a single-blind placebo-controlled randomized crossover study with 2 treatments: CLS-on versus CLS-off (accelerometer only). Each enrolled patient will receive both treatments for 3 months. The order of treatments will be randomized 1 :1.

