## Randomization

[figure not shown]
There will be a 50:50 randomization, with half the subjects randomized to CLS-on then CLS-off, and half randomized to CLS-off then CLS-on.

Subjects previously receiving rate-responsive pacing with CLS that are randomly selected to CLS-on will continue with the identical programmed parameters. For subjects not previously receiving rate-responsive pacing with CLS that are randomly selected to CLS-on nominal programming will be utilized with a base rate of 60 beats per minute.

Subjects will then initiate treatment A (CLS-on or CLS-off) in a blinded fashion. During the testing period, subjects will be tracked with the implanted device accelerometer to quantify physical activity. At 3 months, all subjects will undergo testing as noted below.

- 24 hour Holter monitoring with spectral analysis
- Cycle-ergometer stress with cardiopulmonary gas exchange analysis
- Free form activities with cardiopulmonary gas exchange analysis (staircase, walking, sweeping, suitcase lifting with right and left arms, etc.)
- ANSAR testing (hand grip, Valsalva, deep breathing, and orthostatic challenge)
- Mental stress test with continuous electrocardiographic recording
- Quality of life questionnaire (SF-36/Somerville index)

After 3 months of treatment A, subjects will be reprogrammed to treatment B. Tracking of physical activity with the device accelerometer will continue during this period. After 3 months of treatment B, repeat testing will be repeated as described above. At the conclusion of the study, patients will be asked which pacing mode is preferred.

Patients will be followed during both treatment phases per usual clinical routine. Patients who experience significant symptoms (extreme fatigue, debilitating palpitations, or other clinically relevant symptoms) will be evaluated by their treating physician. Subjects that have any adverse events during treatment A will discontinue treatment A and immediately crossover to treatment B. Subjects with events during treatment B will be removed from the study and unblinded. Further treatment will be determined by the treating physician.

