#### 10.0 Statistical Considerations

##### Sample Size Estimation and Power Analysis

The primary endpoint of this randomized controlled 2x2 cross-over trial will be to measure the influence of autonomic function on heart rate response, and to show an equivalent response for both epicardial and transvenous CLS pacemaker systems. The objective of this study is to evaluate changes in heart rate in response to the CLS algorithm versus a standard accelerometer during various tests of autonomic function. Previous studies of adults with chronotropic incompetence using the CLS algorithm have demonstrated a mean increase in heart rate of  $16.1 \pm 1.1$  beats/minute during mental stress with CLS-on versus  $5.8 \pm 0.6$  beats/minute with standard accelerometer ( $p<0.001$ ).

A further pilot study using ANSAR demonstrated a mean increase in 12.5 beats/minute during isometric hand-grip with CLS-on versus 2.9 beats/min with standard accelerometer ( $p=0.004$ ), 13.2 beats/minute during deep breathing versus 2.9 beats/minute ( $p=0.004$ ), 16.0 beats/minute during Valsalva maneuver versus 4.5 beats/minute ( $p=0.004$ ), and 14.9 beats/minute for postural change versus 6.2 beats/minute ( $p=0.039$ ). The results of the prior pilot study are summarized below.

ANSAR HEART RATE	Baseline	DOD-CLS	DDD	T test	Wilcoxon test
Resting	55.8	70.0	60.8	<0.001	0.004
Isometric Handgrip	59.4	71.9	62.3	<0.001	0.004
Deep Breathing	58.0	71.2	60.9	<0.001	0.004
Valsalva maneuver	57.1	73.1	61.6	<0.001	0.004
Postural Change	58.1	73.0	64.3	0.015	0.039

From Pavri et al. Circulation 2006;114;II 749. 

A two-sided t-test achieves 80% power to infer that the mean difference is not 0 when the total sample size of a cross-over design is 40 (or 81% when n=24 and 96% when n=30) assuming a 5% type I error. The actual difference and the square root of the within mean square error are assumed to be 10. Considering a drop-out rate of 30%, a total of 57 patients will need to be enrolled to achieve the target sample number.

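### The trial is sized with a cross-over t-test, but the SAP's only test sentence compares undefined group means by ANOVA or Kruskal-Wallis and names no patient or period term

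*Combined protocol and SAP*

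**What the plan says.** Section 10.0 (Sample Size Estimation and Power Analysis) opens with "The primary endpoint of this randomized controlled 2x2 cross-over trial". Section 5.0 says "Each enrolled patient will receive both treatments for 3 months", and section 6.0 (Randomization) has "half the subjects randomized to CLS-on then CLS-off, and half randomized to CLS-off then CLS-on". Every patient who completes therefore supplies one CLS-on and one CLS-off value for each outcome.

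The sample size is built on that pairing. For a total of 40 patients, section 10.0 has "A two-sided t-test achieves 80% power to infer that the mean difference is not 0 when the total sample size of a cross-over design". It takes a true difference of 10 and, for the error term, "the square root of the within mean square error are assumed to be 10".

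The Statistical Analysis Plan that follows is one paragraph. Its only sentence naming a test is "Differences between group means for continuous variables will be examined using ANOVA or Kruskal-Wallis Test". It also promises p-values and 95% confidence intervals, and adjusted versions for multivariate analyses, but names no model or covariate for these. No other section supplies an analysis of CLS-on versus CLS-off.

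**The concern.** The sizing relies on each patient acting as his or her own control, and the analysis sentence does not say that this will be kept. Whether the named tests are valid depends on what a group is:

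- **Pacing mode, with patient and period in an ANOVA.** This is a cross-over ANOVA and is valid. The SAP does not say it is meant, and it has no Kruskal-Wallis counterpart on raw values.
- **Pacing mode, on raw values with no patient term.** Both tests treat two measurements on one patient as if they came from two patients.
- **Randomized sequence, on within-patient period differences.** Both tests are valid, but the SAP never mentions period differences.
- **Epicardial versus transvenous route.** The patients are independent, so the tests fit, but CLS-on versus CLS-off then has no stated method.

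At stake are the precision that the cross-over was chosen for and the calibration of the promised p-values and intervals. The choice among these readings is also left open until the data are in hand. The same sentence is the only stated test for the continuous secondary outcomes in section 2.0, for which no sample size is given.

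**Working it through.** **Inputs from section 10.0:** difference 10 bpm, within-patient SD (σw) 10, two-sided 5% level, n = 40 completers, taken as 20 per sequence. **Assumed:** the documents give no between-patient SD, so the within-patient correlation ρ is set to 0.3, 0.5 and 0.7. Data are simulated as normal.

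**1. The plan's own power figures.** The cross-over t-test has SE = σw·√(2/n) and n − 2 degrees of freedom. With the stated inputs it gives 91.1% at n = 24, 96.2% at n = 30 and 99.2% at n = 40. The plan states 81%, 96% and 80%. Only the n = 30 figure is reproduced. That inconsistency is a separate issue, and nothing below rests on it. The within-patient intent is read from the plan's words, not from the one figure that agrees.

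**2. Cross-over precision at n = 40.** SE = 10·√(2/40) = 2.236. Half-width = t(0.975, 38)·SE = 2.024 × 2.236 = 4.53 bpm.

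The comparison of sequences gives the same result. A period difference (period 1 minus period 2) has variance 2 × 10² = 200. The two sequence means differ by twice the mode effect, with SE √(200/20 + 200/20) = 4.472. Half of that is 2.236.

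**3. Raw values treated as independent.** The SD used by the test is the total SD, σw/√(1 − ρ) = 11.95, 14.14 and 18.26. Half-width = t(0.975, 78) × total SD × √(2/40), with t = 1.991. The true SE of the mean difference is still 2.236, so the analysis overstates it by a factor 1/√(1 − ρ) = 1.20, 1.41 and 1.83.

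**4. Rejection rates at n = 40,** by simulation with 100,000 trials per cell; a separate re-run with 20,000 per cell agreed to within simulation error:

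| | ρ = 0.3 | ρ = 0.5 | ρ = 0.7 | Cross-over analysis |
|---|---|---|---|---|
| 95% CI half-width, bpm | 5.32 | 6.30 | 8.13 | 4.53 |
| Rejection at no difference, raw ANOVA | 2.0% | 0.7% | under 0.1% | 5% |
| Rejection at no difference, raw Kruskal-Wallis | 2.1% | 0.8% | 0.1% | 5% |
| Power at 10 bpm, raw ANOVA | 98% | 95% | 79% | 99% |
| Power at 10 bpm, raw Kruskal-Wallis | 97% | 93% | 76% | 99% |

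**5. The same tests on the right variable.** Applied to within-patient period differences between the two sequences, ANOVA rejects 5.05% at no difference and 99.2% at 10 bpm. Kruskal-Wallis rejects 4.9% and 98.8%. The whole loss in the table comes from the input variable, which the SAP leaves unstated.

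**The case against.** The best defence is that this is loose wording and not a wrong test. The SAP does not say one-way ANOVA. The paragraph just before it, in the same section, calls the trial a cross-over and uses the within mean square error, which is ANOVA vocabulary. Nothing in the SAP withdraws the cross-over t-test. On the ANOVA half of the sentence this stands: the fault there is under-specification. It does not cover the Kruskal-Wallis half, which has no valid use on raw CLS-on and CLS-off values. The sentence on multivariate analyses does not help, since it names no model.

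The defence can also say that the harm is modest and rests on an assumed correlation. That stands too. Even under the worst reading, ANOVA power at 10 bpm is 95% or more for a correlation up to 0.5. At 0.7 it is 79%, close to the 80% that the plan states for n = 40.

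A reader might go further and infer that the sponsor has committed to an unpaired analysis, that false positives would follow, or that the trial becomes underpowered. The documents support none of these. The text is open to a valid reading. With positively correlated values the test rejects too rarely, not too often. The power loss is material only if the correlation is high, and the documents do not give it.

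**Conclusion.** The point holds as a mismatch between design and analysis text that should be fixed. The trial is sized on a within-patient contrast. The SAP does not state that contrast, does not define its groups, and offers a non-parametric alternative that is invalid on the raw paired values.

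If the tests were run on raw values with 40 completers, intervals would be wider by a factor of about 1.2 to 1.8 (5.32/4.53 to 8.13/4.53). A nominal 5% test would run at about 2% down to under 0.1%. These sizes rest on the plan's within-patient SD of 10 and on assumed correlations of 0.3 to 0.7. That the error is conservative rests on the correlation being positive, which is to be expected for repeated measurements on one patient. It costs precision and does not produce a false claim of benefit.

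The inconsistent power figures and the analysis of epicardial versus transvenous equivalence are separate issues.

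**What to change.** In the Statistical Analysis Plan, replace the test sentence for CLS-on versus CLS-off with the following:

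- **Main analysis:** a cross-over mixed model with mode, period and sequence as fixed effects and patient as random. Report the period-adjusted within-patient mode difference with its 95% CI. For complete pairs this equals half the between-sequence difference in mean period differences (a cross-over ANOVA gives the same). With incomplete patients the mixed model also uses their single-period data. Such patients are likely, given the planned 30% drop-out and the rule "Subjects with events during treatment B will be removed from the study and unblinded", so the mixed model should be named as the main analysis.
- **Non-normal outcomes:** the Wilcoxon rank-sum test on within-patient period differences between the two sequences, not on raw values. With two groups, Kruskal-Wallis is the same test apart from the continuity correction.
- **Between-patient comparisons only:** keep ANOVA or Kruskal-Wallis on single values, and define the groups for each test.

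The cost is SAP wording, settled before the data are analysed. No new data, visits or patients are needed. This change does not settle the epicardial versus transvenous aim.

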## 11.0 Privacy/Confidentiality Issues

Only individuals directly involved with the study will have access to data. Information is for research purposes only and will be used for publication purposes. All participants will have their names concealed. Access to identified patient information will be limited to the investigators listed within this IRB application. De-identified information with HIPPA identifiers removed will be available to other investigators following appropriate IRB approval. Confidentiality and security will be maintained for the database. The database is stored behind a firewall (in addition to the institutional firewall) with the highest level of protection, i.e. the same level of protection as the on-line hospital information system at UCLA. This means that users must logon to a web server that sits between the institutional firewall and the firewall to the database, and only this application server is allowed to query the database. Only users approved through our institutional review board will be allowed access to patient identifiers. Other levels of authorization may exist for future approved users following IRB approval, e.g. access to de-identified data.

Data is initially collected in the medical record for each individual study participant. The information will be extracted from the patient's medical record and then transferred into the Case Report Form (CRF).

The CRFs will include personal identifiers for participant. However, this data will not be accessible as numbers and initials are assigned for each participant and these will become the identifying information for each study participant. A master list with patient demographics will only be accessible to the principle investigator and his senior coinvestigator. This data will not be available to others.

### 13.0 Follow-up and Record Retention

The study will continue for 5 years. The data will be maintained for 3 years after completion of the study.

